#### **Project Summary**

The multi-disciplinary UPMC Post-COVID Recovery clinic serves the clinical needs of Long-COVID patients, those with persistent symptoms after initial infection recovery. Using an IRB-approved research registry collecting biomarkers, clinical data, imaging results and patient-reported outcomes (PROs), this group defines burden of long-COVID and guides personalized medicine strategies.

To date, phenotyping of 148 Long-COVID patients show 86% with new onset cognitive fog (using validated criteria) and 48% with depression (PHQ8 criteria). Cognitive fog was the most common complaint endorsed by patients during their clinic evaluations. ***Additionally, a subgroup of patients requesting a behavioral evaluation, who were in the prime of their adult productivity, reported that "cognitive fog" was the main symptom impacting their functioning, work performance, and life satisfaction; making it a critical domain to target clinically.*** The specific cognitive deficits reported as part of this "fog" varied across patients.

In a pilot study, we prescribed 90 of these depressed patients a coached digital cognitive behavioral therapy (dCBT) app developed by UPMC called RxWell, as part of care. Half of the patients (N = 45) downloaded the app and the 75% who completed techniques showed improvement in depression over 3 months (large effect size of change with PHQ8 (delta 6; p=0.001; Cohen's d=1.1; mean age 46)).

We posit rapid, accurate, and scalable assessment of cognitive impairment and implementation of the right interventions targeting specific deficits is a better fuller recovery path for these patients. ***This proposal evaluates the utility of computer-based evaluation of COVID-related cognitive fog and the relative efficacy of two intervention strategies to treat moderate cognitive impairment using a randomized trial which will inform the design of a future adaptive trial.*** We plan to study 120 post-COVID patients seen in the Long-COVID clinic over the next 12 months with moderate or severe cognitive fog to assess the type and severity of neurocognitive impairment using computerized neuropsychological testing (BrainCheck). We will randomize to either 1) dCBT with coaching (RxWell) versus 2) stimulant medication (amphetamine/dextroamphetamine), as part of the study embedded in clinical care, to provide data to inform design of future larger phase adaptive trials. BrainCheck is

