#### **Summary of Project**

Design Summary: Randomized trial of dCBT versus stimulant to treat cognitive impairment +/- depression in adults with Long-COVID.

Aim 1: Test efficacy of two interventions for improving cognitive impairment (primary outcome) and emotional distress (depression), life satisfaction, work disability, and medical utilization (secondary

outcomes). Assess effect of demographic and COVID symptom characterization variables on treatment efficacy.

Hypothesis: Stimulant therapy will outperform dCBT for patients with cognitive impairment alone and dCBT will outperform stimulant for cognitive impairment and depression.

Aim 2: Define the important response characteristics in these patients to inform design of a larger adaptive clinical trial evaluating treatment options for COVID-related cognitive impairment.

Methodology: Participants with confirmed Long-COVID cognitive impairment assigned with a 1:1 allocation to either arm using a permuted block design stratified by depression severity. Participants will complete computerized neurocognitive assessments and other study measures at baseline, 1.5 (interim) and 3 months after randomization.

Inclusion: Patients with Long-COVID between ages of 21-65; moderate cognitive impairment (MOCA $\leq$ 18) present for at least 3 months; access to a smartphone.

Exclusion: No history of dementia, psychosis, mania, addiction or current conditions requiring immediate hospitalization. No history of stimulant failure. No current cardiac condition

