#### **Primary outcome: Cognitive impairment**

Measures:

Montreal Cognitive Assessment (MOCA) (10 minutes) A validated screening tool for detection of mild cognitive impairment.

BrainCheck Neurocognitive Assessment (15 minutes): FDA-approved validated automated remote neurocognitive assessments in multiple domains.

ImPACT (20 minutes) is an FDA-approved computerized neurocognitive concussion assessment tool.

Secondary outcomes: depression (PHQ8), satisfaction with life (SWLS), disability (Sheenan Disability Scale), and health care utilization (ED and outpatient visits).

Statistical Analysis:

Aim 1: Intent-to-treat analyses stratified by depression severity. We evaluate three-month outcomes using linear regression models with assigned intervention depression severity and the corresponding baseline score as independent variables. Longitudinal linear mixed effects regression models with time, intervention, depression severity and corresponding baseline scores will assess treatment effects at 1.5 and 3 months and with interactions between intervention and time-points tested. Multivariable models include prespecified demographic and COVID symptom characteristics as covariates.

Aim 2: We will build a seamless Phase 2 to Phase 3 design with defined decision rules to determine whether interventions, including dCBT and stimulant, will “graduate” to the Phase 3 adaptive clinical trial. Bayesian analyses of accumulated data (including data from Aim 1) are performed on a prespecified schedule until stopping criteria are met. For a comparison of interventions, we may conclude superiority, inferiority or futility which can depend on pre-defined stratification variables. We anticipate that a response adaptive randomization (RAR) will be applied in Phase 3 such that the proportion of participants who receive each intervention will be determined based on the predicted probability that the intervention is optimal considering all accrued outcome data. Findings from Aim 1 will be used in simulations to estimate sample size requirements and to evaluate the operating characteristics of the adaptive clinical trial.

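### Aim 1 asks how demographic and COVID symptom variables affect treatment efficacy, but the analysis section states no term that would estimate this

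*Combined protocol and SAP*

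**What the plan says.** The objective is in the Summary of Project, under Aim 1. After naming the outcomes, it adds: "Assess effect of demographic and COVID symptom characterization variables on treatment efficacy".

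The analysis is in the section on the primary outcome, under Statistical Analysis, Aim 1. It has four relevant parts:

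- An opening statement: "Intent-to-treat analyses stratified by depression severity".
- A three-month analysis by "linear regression models with assigned intervention depression severity and the corresponding baseline score as independent variables".
- A longitudinal mixed model with time, intervention, depression severity and baseline score, with "interactions between intervention and time-points tested".
- One sentence on the demographic and COVID variables: "Multivariable models include prespecified demographic and COVID symptom characteristics as covariates".

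The variables in the last item are described as prespecified, but the document does not list them. The Project Summary gives the size ("We plan to study 120 post-COVID patients") and the Summary of Project gives the allocation ("1:1 allocation to either arm using a permuted block design stratified by depression severity").

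Aim 2 is to define response characteristics that will inform a later adaptive trial. Its analysis text says that Aim 1 findings will feed the simulations for that trial, and that its conclusions may depend on stratification variables defined in advance.

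**The concern.** The object of the Aim 1 sentence is treatment efficacy, not outcome. It asks whether the difference between stimulant and dCBT changes with, say, age or COVID symptom profile. A variable entered as an ordinary covariate answers a different question: who does better or worse whichever treatment is given. It also sharpens the overall treatment estimate. Neither result shows how the treatment difference varies.

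A stated part of Aim 1 would therefore end without an estimate. Aim 2 would also lack an input it could use. Deciding which patient characteristics should shape the simulations or strata of the later trial calls for estimates of differential benefit, and prognostic coefficients are no substitute.

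**Working it through.** **1. Objective against model.** Write T for intervention, X for a demographic or COVID symptom variable, and B for baseline score (depression stratum omitted for brevity). With X as a covariate:

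E[Y] = b0 + b1·T + b2·X + b3·B

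The treatment effect at any value x is E[Y | T=1, x] − E[Y | T=0, x] = b1, which does not depend on x. With a product term added:

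E[Y] = b0 + b1·T + b2·X + b3·B + b4·T·X

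The treatment effect at x becomes b1 + b4·x. The Aim 1 sentence asks about b4. The stated analysis reports b1 and b2.

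**2. Does other text supply b4?**

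| Analysis stated | What it can show |
|---|---|
| Three-month regression | Average treatment effect, adjusted for depression severity and baseline |
| Mixed model with intervention-by-time interaction | Whether the treatment effect differs between 1.5 and 3 months |
| Analysis stratified by depression severity | Treatment effect by depression stratum, if run separately in each |
| Multivariable models | Prognostic associations and an adjusted average effect |

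No row gives a treatment effect by demographic or COVID symptom variable.

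**3. What the trial could estimate if the term were added.** The document gives N = 120 and 1:1 allocation. It gives no SD, significance level, power, effect size or dropout, so there is no figure of its own to reproduce. Assumptions: two-sided 5% significance, 80% power (multiplier 1.96 + 0.84 = 2.80), SD = 1, a binary moderator with share f in one level, arms balanced within each level, and no dropout.

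- Main effect: SE = sqrt(4/120) = 0.183 SD; detectable effect 2.80 × 0.183 = 0.51 SD.
- Interaction, that is, the difference between the two subgroup treatment effects: SE = sqrt(4/(120f) + 4/(120(1−f))).
- f = 0.5: SE = sqrt(4/60 + 4/60) = 0.365 SD; 95% CI half-width 1.96 × 0.365 = 0.72 SD; detectable interaction 2.80 × 0.365 = 1.02 SD.
- f = 0.3: detectable interaction 1.12 SD. f = 0.2: 1.28 SD.
- Power for a 0.5 SD interaction: Φ(0.5/0.365 − 1.96) = Φ(−0.59) ≈ 28% at f = 0.5, falling to about 19% at f = 0.2.

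**4. Sensitivity of the 1.02 SD figure (f = 0.5).** Losing 15% to 20% of patients (N = 102 to 96) raises it to 1.11 to 1.14 SD. Baseline adjustment multiplies it by sqrt(1 − r²): 0.89 SD at r = 0.5 and 0.73 SD at r = 0.7.

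**The case against.** **Covariates could include product terms.** The wording does not exclude them, so a reader who infers that the planned models are incapable of estimating effect modification goes too far. What stands is narrower: no such term is stated for these variables, although the intervention-by-time interaction is spelled out.

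**Heterogeneity is examined.** It is tempting to conclude that the plan looks at no variation in treatment effect. That is wrong. The analysis stratified by depression severity can give separate effects for the one moderator in the stated hypothesis ("Stimulant therapy will outperform dCBT for patients with cognitive impairment alone", reversed when depression is present). The document also treats emotional distress as a consequence of COVID, so the boundary between depression and COVID symptom variables is not sharp. This still leaves the demographic variables and the other COVID symptom variables uncovered.

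**The aim may loosely mean prediction of outcome.** Possible, though not the natural reading. In that case the aim needs rewording, and the two sections still have to be reconciled.

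**The next phase does not depend on this.** A reader might infer that the personalised next phase would be built on the wrong variables. The problem statement ties personalisation to cognitive domains of impairment, and depression severity is the only stratification variable named. The documents do not support that inference. The link that holds is to Aim 2's response characteristics and simulations.

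**A dramatic example proves little.** One can simulate effects of +0.5 and −0.5 SD in two equal halves. The covariate-only treatment coefficient then averages about zero and is significant in about 5% of trials. But the true average effect there is zero, so this is correct behaviour for a test of the average. The case is a constructed extreme, and its 1.0 SD interaction lies almost at the detectable limit, which flatters the remedy. The 28% power at 0.5 SD is the more sober guide.

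**Conclusion.** The point holds as a mismatch between a stated objective and the stated analysis. Aim 1 asks how efficacy varies with demographic and COVID symptom variables, and no term in the Statistical Analysis section estimates that. This follows from the form of the model and needs no assumption about effect sizes.

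Its reach is limited. The overall comparison of stimulant with dCBT is not affected, nor is the depression-stratified analysis. Adding the missing terms would make the question estimable, but not confirmable at this sample size: about 1.02 SD detectable for a 50:50 moderator, and more for unequal splits or with dropout. Those figures rest on the assumed SD, significance level, power and completeness, none of which the document states. The sponsor should correct this before analysis. It does not threaten the trial's main result.

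**What to change.** In Statistical Analysis, Aim 1:

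1. List a short set of demographic and COVID symptom moderators by name, so that the number of interaction tests is fixed in advance.
2. For each moderator, one at a time, add an intervention-by-moderator term to the three-month model, keeping depression stratum and baseline score. If moderation at 1.5 months is of interest, carry the term into the longitudinal model, with its interaction with time.
3. Report the treatment effect at each moderator level and the interaction estimate, each with a 95% confidence interval, labelled exploratory.
4. Keep the covariate-only model for the adjusted overall effect, and describe its covariate coefficients as prognostic.

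Alternatively, if effect modification was not intended, reword the Aim 1 sentence as prediction of outcome.

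The cost is a few lines of text and a few more models on data already planned, with no change to design, visits or treatment. The drawback is imprecision: under the assumptions above, a 95% interval of about ±0.72 SD around an interaction for an evenly split moderator. The plan should say so, so that a non-significant interaction is not read as evidence of a uniform effect.
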